2.10 Data analysis

Statistical analysis will be performed using SPSS and Excel software. Data will be calculated and graphed as mean plus minus standard error of mean (SEM).

Metric variables will be reported by mean and standard deviation resp. median and IQR, categorical variables will be reported by frequencies per group and timepoint. The primary outcome subjective symptom improvement after 12 months in either group will be analyzed by a t-test or a Man-Whitney-U-test depending on the distribution of improvements.

For the secondary endpoints, differences of rates of adverse events between the two treatment groups will be analysed by a Chi-squared test. Blood loss, use of pain killers and changes in condition-specific quality of life will be compared between groups analogously to the primary outcome.

Changes in POP-Q values from baseline over time will be analysed by a linear mixed model with fixed effects group, time, POP-Q point, age and BMI and random effect intercept per patient. Statistical significance will be set 0.05. No correction for multiple testing is performed because only one main hypothesis is considered.

3. Research facility

The patient screening will be performed at the urogynaecologic outpatient clinic of the Department of General Gynaecology and Gynaecologic Oncology, Medical University of Vienna, Austria. Infrastructure needed for this study is already present.

4. Ethical and legal aspects

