2.2 Study design

This trial is a single-centre, prospective, randomized trial conducted with the aim of determining the superiority of non-absorbable prolene over absorbable PDS suture material with regard to the primary outcome in POP patients undergoing sacrospinous hysteropexy. The study will be a single-blind study, as it is impossible to blind the study surgeon for the surgical procedure to which the subject is assigned. However, all outcome assessors and the subjects will be blinded to the assigned treatment. Postoperative follow-up will take place after 4-6 weeks, 6 months and 12 months. Patients will undergo a standardized urogynaecologic examination that includes assessment of prolapse with POP-Q measurement [12]. Furthermore subjective outcome will be assessed with standardized questionnaires – our study participants will receive the German version of the pelvic floor questionnaire [11].

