2.5 Randomization

Randomization will be performed by the randomizer of the Medical University of Vienna; subjects will be stratified by parity (Primipara / Multipara) and randomized in blocks of four. All subjects will receive a unique study number.

To prevent unmasking the actual procedures, the medical records will indicate the actual surgical procedure without stating the suture material used for anterior colporrhaphy. Intraoperative data collection will be conducted by the study surgeon rather than by other research staff.

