2.9 Sample size and power considerations

Alteration of the prolapse domain score obtained from the pelvic floor questionnaire before and after intervention (between baseline and 12 months follow-up) will be compared between patients receiving continuous stitches versus simple interrupted stitches for anterior colporrhaphy. Schoenfeld et al. observed a mean prolapse domain score of 3.33 with a standard deviation of 2.2; we assume that the standard deviation of the pre- and post-interventional treatment will be equal, and that the correlation between the two values is 0.5, resulting in a standard deviation of the change between pre- and post-interventional value will be 2.2.; then, with 21 patients per group a difference of 2 between the changes in the two groups can be identified

with 80% power. Taking into account an expected dropout rate of 20%, 26 patients will be included per group.

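### The primary test is unadjusted and its form is left to the observed distribution; one pre-specified ANCOVA on baseline score and parity would raise power from 82% to 91% on the plan's own assumptions

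*Combined protocol and SAP*

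**What the plan says.** Section 2.10 states that improvement after 12 months "will be analyzed by a t-test or a Man-Whitney-U-test depending on the distribution of improvements". It names no normality check, threshold or other rule for choosing between the two tests, and no covariate. It adds: "Statistical significance will be set 0.05". It does not say whether the test is one- or two-sided. Pain-killer use, blood loss and change in quality of life are to be compared in the same way as the primary outcome.

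Section 2.9 makes clear that the quantity compared is the change from baseline to 12 months. It takes an SD of 2.2 before and after surgery, assumes that "the correlation between the two values is 0.5", and concludes that "with 21 patients per group a difference of 2 between the changes in the two groups can be identified" with 80% power.

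Under Data collection (section 2.8), the same questionnaire is completed at baseline and at each follow-up. In section 2.5, "subjects will be stratified by parity (Primipara / Multipara) and randomized in blocks of four". Parity enters no analysis. The only adjusted model in the plan is the mixed model for POP-Q values, a secondary outcome, which includes age and BMI.

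**The concern.** There are two problems in the one confirmatory test.

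First, the change score does not remove the influence of baseline. With equal SDs and a correlation of 0.5, change still depends on baseline with slope 0.5 − 1 = −0.5: women who start with worse scores improve more on average. An unadjusted test leaves that variation in the error term. A baseline difference between arms that arises by chance then moves the estimate. With about 21 analysed women per arm, the lost precision matters.

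Second, the test depends on the observed distribution, with no stated rule. The trial was powered for a mean difference of 2 points. A Mann-Whitney test compares ranks and does not estimate that difference. Two analysts could both follow section 2.10 faithfully and report different primary tests and p-values.

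The planned power also depends on a correlation of 0.5 for which the plan gives no source. If surgery weakens the link between the scores before and after, the change-score test loses power quickly.

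**Working it through.** **Inputs.** From section 2.9: SD 2.2 at each time, correlation r = 0.5, difference 2, 21 evaluable women per arm. From section 2.10: significance level 0.05. Assumption: two-sided, which best reproduces the plan's 21 per arm (a one-sided t-test would have 89.4% power). Power is from the noncentral t distribution.

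**The plan's own figure.**
- SD of change = √(2 × 2.2² × (1 − 0.5)) = 2.2.
- Standard error of the group difference = 2.2 × √(2/21) = 0.679, so the noncentrality is 2/0.679 = 2.95 on 40 df.
- Power = 82.0%. With 20 per arm it is 79.997%, so 21 is the first number to reach 80%. The plan's figure is reproduced.

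**ANCOVA with baseline score and parity.**
- Residual SD = 2.2 × √(1 − 0.5²) = 1.905.
- Standard error = 1.905 × √(2/21) = 0.588, so the noncentrality is 2/0.588 = 3.40 on 42 − 4 = 38 df.
- Power = 91.2%. ANCOVA would need 16 per arm for 81.8%.
- Variance ratio of ANCOVA to change score = (1 − r²)/(2(1 − r)) = (1 + r)/2 = 0.75, a 25% reduction.

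A simulation with normal scores and no parity effect (20,000 trials) gave 81.8% for the t-test, 79.6% for Mann-Whitney and 90.7% for ANCOVA.

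**Precision.** The 95% half-width is 2.021 × 0.679 = 1.37 for the change score and 2.024 × 0.588 = 1.19 for ANCOVA. The difference detectable with 80% power falls from 1.95 to 1.69.

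**Dependence on the correlation** (score SD 2.2, 21 per arm, difference 2):

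| r | t-test on change | ANCOVA |
|---|---|---|
| 0 | 52.9% | 81.9% |
| 0.3 | 68.1% | 85.3% |
| 0.5 | 82.0% | 91.2% |
| 0.6 | 89.5% | 94.8% |
| 0.7 | 96.0% | 98.0% |
| 0.8 | 99.5% | 99.8% |

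**Chance imbalance.** The standard error of the baseline difference between arms is also 2.2 × √(2/21) = 0.68. An imbalance of that size shifts the unadjusted difference in change by 0.5 × 0.68 = 0.34 points, and 0.34/2 = 17% of the planning difference. This illustrates the noise already counted in the power loss; it is not a further harm.

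**Role of parity.** ANCOVA with baseline alone (39 df) has 91.26% power; adding parity (38 df) gives 91.22%. The documents give no prognostic strength for parity, so the whole computed gain comes from the baseline score. Parity belongs in the model because randomisation was stratified on it.

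**Bounded score.** The domain score runs from 0 to 10 and may pile up at zero after surgery. This was simulated with scores clipped to that range, under assumed values: latent SD 2.2, r = 0.5, baseline mean 5, latent shift 2. With a control-arm latent mean of 3.33 at 12 months, power was about 73% (t-test), 70% (Mann-Whitney) and 87% (ANCOVA). With a mean of 2 it was about 56%, 52% and 83%, and ANCOVA's type I error was 4.8%. The floor therefore widens the gap.

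**The case against.** The strongest reply is that this is mainly a matter of efficiency. A t-test on change is valid and unbiased under randomisation, holds its type I error, and is the analysis that section 2.9 powered; it reaches the stated target. Chance imbalance is random and already part of its standard error. All of that stands, and it is why the point is a recommendation and not a claim that the primary result would be invalid.

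The gain also depends on the correlation. Nothing in the documents shows that it is below 0.5, and at 0.7 or 0.8 there is little to win. That stands too, but the variance ratio (1 + r)/2 never exceeds 1, so under the plan's equal-SD assumption the only cost is two degrees of freedom.

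On test selection, simulating one fixed rule (Shapiro-Wilk in each arm, then t-test or Mann-Whitney) gave type I errors of 5.0% to 5.3% and power of 81.8%, so there is no evidence of excess false positives under such a rule. The plan states no such rule, however, and the quantity being estimated still changes with the choice. What remains is a gap in pre-specification.

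**Conclusion.** The concern holds. The primary analysis is unadjusted, and its form depends on the observed distribution without a rule. Nothing elsewhere in the documents supplies an adjustment or a rule.

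On the plan's own assumptions, ANCOVA adds about 9 percentage points of power at 21 per arm (82.0% to 91.2%). The gain ranges from 29 points at a correlation of 0 to near zero at 0.8. ANCOVA stays above 80% across that range, while the change-score test reaches 80% only if the correlation is about 0.5 or more.

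These figures assume a two-sided 5% test, equal SDs of 2.2, a linear relation between the two scores, approximately normal residuals and a model-based standard error. The change should be made, but the trial does not fail without it.

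**What to change.** Replace the primary-analysis sentence in section 2.10 with one analysis fixed before the 12-month data are examined:

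- ANCOVA of the 12-month prolapse domain score on treatment, baseline score and parity stratum, tested two-sided at 5%, reporting the adjusted mean difference with its 95% confidence interval.
- One named standard error method to allow for the bounded score, for example the HC3 robust standard error. It would give up a little of the 91.2%, which was computed with the model-based standard error.
- Mann-Whitney on the change scores as a sensitivity analysis only.
- The same model, with the matching baseline score, for the other questionnaire domains.

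The cost is a wording change and two degrees of freedom (40 to 38). The covariates are already collected, no additional patients are needed, and SPSS, which the plan already names, fits the model.

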2.8 Primary and secondary outcome measures

The primary outcome is subjective symptom improvement (evaluated by the prolapse domain score of the Deutsche Beckenboden Fragebogen) assessed at 12 months after surgery.

The secondary outcomes are the anatomical outcomes (the rate of suboptimal anatomical outcome in each compartment (POP-Q point, change in POP-Q values from baseline), condition-specific quality of life (any changes in questionnaire Deutscher Beckenboden Fragebogen from baseline), postoperative complications (haematoma, vesico-vaginal fistula, ureteral obstruction, urinary tract infection, incomplete bladder emptying, overactive bladder or stress incontinence symptoms, suture erosion, vaginal wound dehiscence, infection or granulation tissue, etc), and use of pain killers during the hospital stay. In addition, patients' pain level will be assessed through the standardised Visual Analog Scale (VAS), Numeric Rating Scale (NRS) [13] and the earlier specified questions, patients' improvement rate will be assessed through the "Patient Global Impression of Improvement (PGI-I).

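### The primary test is chosen between a t-test and Mann-Whitney from the observed improvements, with no criterion or default, although the trial is sized on a difference in mean change

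*Combined protocol and SAP*

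**What the plan says.** Section 2.8 (outcome measures) defines a single primary outcome: "The primary outcome is subjective symptom improvement (evaluated by the prolapse domain score of the Deutsche Beckenboden Fragebogen) assessed at 12 months after surgery". Section 2.10 states that this outcome "will be analyzed by a t-test or a Man-Whitney-U-test depending on the distribution of improvements". It names no normality test, cut-off, pooled or per-arm check, blinded review or default, and no other section supplies one. It attaches no effect measure or confidence interval to either test, and it waives multiplicity adjustment on the ground that there is one main hypothesis.

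Section 2.9 sizes the trial on the change from baseline to 12 months: "with 21 patients per group a difference of 2 between the changes in the two groups can be identified", at 80% power. Section 2.10 then says that blood loss, pain-killer use and changes in condition-specific quality of life "will be compared between groups analogously to the primary outcome", so they inherit the same open choice.

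**The concern.** The improvements exist only once the 12-month data are in, so the one confirmatory test is fixed after its outcome can be seen. The two tests also answer different questions. The t-test compares mean change, the quantity behind Section 2.9. Mann-Whitney asks whether one arm tends to rank higher. It addresses the same quantity only if one arm's distribution is a pure shift of the other's, which the plan does not assume.

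Two things are at stake. Without a rule, either p-value can be defended as the planned one. And if the arms differ in shape, the result may not bear on the difference that the trial was sized to detect.

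**Working it through.** **Inputs from Section 2.9.** The cited study "observed a mean prolapse domain score of 3.33 with a standard deviation of 2.2"; the plan takes the same SD before and after surgery and assumes "the correlation between the two values is 0.5"; the difference is 2, with 21 evaluable per group. Section 2.10 gives a significance level of 0.05 without sidedness. Two-sided is assumed, because a one-sided test (15 per group by normal approximation) does not reproduce 21.

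**The plan's own figure.**
- SD of change = √(2.2² + 2.2² − 2 × 0.5 × 2.2 × 2.2) = √4.84 = 2.2, as stated.
- Noncentrality at 21 per group = 2 / (2.2 × √(2/21)) = 2 / 0.679 = 2.95. With 40 degrees of freedom, power is 82.0%. With 20 per group it is 79.997%. The smallest n reaching 80% is therefore 21, which is a t-test size for a difference in means.

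**Effect of the choice.** The plan gives no rule, so one was assumed: Mann-Whitney if Shapiro-Wilk p < 0.05 in either arm, otherwise the t-test. Each scenario has 20,000 simulated trials, 21 per arm, two-sided 0.05. The simulation standard error is √(0.05 × 0.95 / 20,000) = 0.15 points near 5%. Entries are percentages of trials; the first four numeric columns are rejection rates.

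| Change scores (assumed shapes) | t-test | Mann-Whitney | Normality rule | More favourable p | Tests disagree |
|---|---|---|---|---|---|
| Normal, SD 2.2, no effect | 5.1 | 5.1 | 5.3 | 6.2 | 2.1 |
| Normal, SD 2.2, difference 2 | 81.4 | 79.3 | 81.4 | 82.9 | 5.0 |
| Same skew in both arms (gamma, shape 2), no effect | 4.6 | 4.7 | 5.2 | 6.1 | 2.8 |
| Same skew in both arms, difference 2 | 82.6 | 89.9 | 89.6 | 90.7 | 9.0 |
| Scores bounded 0 to 10, no effect | 4.9 | 4.6 | 5.0 | 5.8 | 2.1 |
| Equal means, gamma (shape 1) against normal | 5.4 | 7.5 | 7.6 | 8.7 | 4.4 |
| Equal means, mirrored gammas (shape 2) | 5.7 | 11.7 | 11.6 | 12.8 | 8.1 |

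Smaller repeat runs under no effect gave 4.6% to 5.6% for the rule and 5.6% to 6.3% for the more favourable p-value.

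**What a single named analysis would give.**
- t-test at 21 per group: 82.0%, as above.
- ANCOVA on baseline: residual SD = 2.2 × √(1 − 0.5²) = 1.905. Noncentrality = 2 / (1.905 × √(2/21)) = 3.40. With 39 degrees of freedom, power is about 91%.
- Mann-Whitney, pure shift: 21 / 0.955 = 22.0 per group under normality. At the lowest relative efficiency, 0.864, it is 21 / 0.864 = 24.3, so 25.

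**The case against.** The strongest reply is that Section 2.10 ties the choice to the distribution, not to the p-value. An analyst who follows that text mechanically keeps type I error near 5% when the arms share a shape and loses no power at the design effect under normality. With a common skewed shape, switching helps: 89.6% against 82.6% for the t-test. All of this stands, and it limits the size of the point. It does not supply the missing rule.

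A second reply is that Section 2.1 hypothesises better improvement without naming a mean, and that under a pure shift both tests address the same quantity. That is fair. But the sizing in Section 2.9 implies a mean difference, and nothing in the plan commits to a pure shift.

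A reader might go further and infer that the switch sharply cuts power when a minority of suspensions fail. One can build such a case. Suppose 20% of one arm fail with mean change −1, everyone else improves by 3.5, and the SD within each component is 1. Power is then 39% for the t-test, 19% for Mann-Whitney and 23% under the rule. The documents do not support these inputs:
- An SD of 1 in the arm without failures conflicts with the planned 2.2. With 2.2 within components, power is about 19% (t-test) and 18% (rule).
- The mean difference is 0.2 × 4.5 = 0.9, not 2. With 44% failures (0.44 × 4.5 = 1.98) and SD 2.2, power is 66.1% and 65.1%.
- An average improvement of 3.5 exceeds 3.33, the only mean score given. If 3.33 is a baseline mean, that improvement is impossible on a scale with a floor of 0. The plan does not say which it is.

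A reader might also infer a large false-positive rate for means. With equal means, one arm with 20% failures and the other uniform, the rule rejects in 27.5%, 11.4%, 7.6% and 6.9% of trials for uniform half-widths of 1, 2, 2.6 and 3. The figure follows the assumed width. Moreover, the arms do differ in these cases, so a Mann-Whitney rejection is correct for unequal distributions. It misleads only if reported as a difference in means.

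**Conclusion.** The point holds at moderate size. The plan leaves the test for its only confirmatory outcome to be settled from the outcome data, with no criterion, and one of the two options does not in general test the difference that the trial is sized for. This should be corrected before anyone sees 12-month data by arm.

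The certain part is the gap in the wording and the mismatch with Section 2.9. The consequences rest on assumed shapes and an assumed switching rule. They amount to error of about 6% if the more favourable test is taken, disagreement in about 5% of trials under normality at the design effect, and rejection above 5% when means are equal but shapes differ by arm. Arm-specific shapes are possible when a resorbable suture is compared with a permanent one on a bounded score, but the documents do not show that they will occur.

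It would be wrong to conclude that the sample size is faulty, that type I error is badly inflated, or that power at the design effect is lost. The plan's figures support none of these.

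**What to change.** In Section 2.10, replace the choice between two tests with one primary analysis, for example: *The primary analysis is the two-sided comparison, at the 0.05 level, of mean change in prolapse domain score from baseline to 12 months, estimated by ANCOVA adjusted for the baseline score and reported with a 95% confidence interval, however the changes are distributed. A Mann-Whitney test with a Hodges-Lehmann shift is a sensitivity analysis and cannot replace the primary result.*

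Only one analysis should be named. Allowing either an unequal-variance t-test or an adjusted version would leave two candidates again. ANCOVA estimates the difference that Section 2.9 sizes for and uses a baseline score already collected.

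For changes in the quality-of-life scores, name one test in advance. Do the same for blood loss and pain-killer use, where a rank test is acceptable because these outcomes are plausibly skewed and are not confirmatory.

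The cost is a few sentences, and 21 per group stands. Against a rank test, an unadjusted mean comparison can lose about 7 to 8 points of power under a common skewed shape. Baseline adjustment at the plan's correlation of 0.5 raises power from about 82% to about 91%, which should largely offset this, though the 91% is calculated under normality. A sponsor who prefers ranks could prespecify Mann-Whitney instead, but would then need about 22 to 25 evaluable per group under a pure shift and an effect measure to match.

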2.1 Study hypothesis

Primary study hypothesis is that patients receiving a sacrospinous hysteropexy with non-resorbable Prolene sutures (study group) experience a better subjective symptom improvement (evaluated by the prolapse domain score of the Deutscher Beckenboden Fragebogen [11]) assessed at 12 months after surgery, than patients with resorbable PDS sutures (control group).

The secondary hypotheses are, that the study group will have:

- better anatomical outcomes (better rate anatomical outcome in each compartment (change in POP-Q values from baseline) [12]),
- better condition-specific quality of life scores (changes in questionnaire from baseline),
- less postoperative complications (haematoma, vesico-vaginal fistula, ureteral obstruction, urinary tract infection, incomplete bladder emptying, overactive

bladder or stress incontinence symptoms, suture erosion, vaginal wound dehiscence, infection or granulation tissue, etc),

- lower use of pain killers for buttock pain during the hospital stay and in the 12 months postoperative period
- lower pain levels (assessed through the standardised Visual Analog Scale (VAS) and Numeric Rating Scale (NRS) [13]) at postoperative day 1, at discharge, at 4 to 6 weeks, 6 and 12 months.

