2.6 Intervention

Sacrospinous hysteropexy will be performed in a traditional and standardized manner in accordance with our surgical policy. Any other concomitant procedures (e.g.,

anterior and/or posterior colporrhaphy, cystoscopy, etc.) will be performed in accordance with each surgeon's preferred technique.

Operative management: All patients will be operated by the vaginal route. They are prepared under strict aseptic conditions in the dorsal lithotomy position. The bladder is emptied preoperatively with a thin disposable catheter and antibiotic prophylaxis (cefazolin) is administered before incision. A vasoconstricting solution (combination of vasopression and NaCl) is administered and a high posterior colpotomy is made towards the posterior cervix. Blunt preparation towards the right Spina ischiadica to visualize the right sacrospinous ligament. Once 4 cm of ligamentum sacrospinale are visualised, two sutures will be placed through the ligament approximately 2 cm medial of the spina ischiadica. Depending on preoperative randomization, patients will receive either PDS sutures (PDS 0) or prolene (2-0) sutures. This suture will then be placed through the posterior cervical wall, but not yet knotted. First, the colpotomy will be closed via absorbable sutures (2/0 vicryl). Should additional procedures such as anterior and/or posterior colporrhaphy be indicated, they will be performed at this stage. Only after, the pre-laid fixation sutures will be tied, whereby the portio will come to lie about 4-6 cm cranial of the level off the vulva towards the sacrospinous ligament. Participating surgeons will be defined as high volume surgeons in prolapse surgery and will also be part of the urogynaecologic core team.

Perioperative management: is also standardized and includes preoperative single-shot antibiotics as well as vaginal pack and an indwelling urinary catheter for 24 hours after the surgical procedure. Patients will have postvoid residual volume measurement at the first postoperative day (when urinary catheter is removed). A postvoid residual volume of $2 \times < 150$ ml is defined as normal and no further follow-ups are necessary. Postvoid residual volumes of > 150 mL or greater will be

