2.7 Inclusion and exclusion criteria

Inclusion criteria

- Anterior vaginal wall prolapse beyond the hymen (POP-Q point Aa or Ba >0) with a central defect.
- Apical vaginal vault prolapse beyond the hymen (POP-Q point C >0) with a central defect. Vaginal bulge symptoms
- Uterus-preserving reconstructive surgery via vaginal sacrospinous hysteropexy is planned

Exclusion criteria

- History of hysterectomy

- Reconstructive pelvic floor surgery using mesh or obliterative surgery is planned
- Reconstructive pelvic floor surgery with hysterectomy is planned
- Prior reconstructive pelvic floor surgery with mesh
- Known pelvic malignancy
- Known inflammatory disease
- Current systemic glucocorticoid or immunosuppressant treatment.
- Subject is unable or unwilling to participate

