2.8 Data collection

At baseline, the following data will be collected: demographics and medical history data (age, body mass index, parity, menopausal and hormone therapy status, nutritional status, current smoking, previous hysterectomy and previous anti-incontinence surgery), and medical comorbidities (diabetes mellitus, connective tissue disorders), and data from the standardized urogynaecologic examination (POP-Q examination during maximal Valsalva, genital hiatus measurements and ultrasound of cervix, uterus, bladder, pelvic floor muscles and levator ani muscle hiatus).

Urogynaecologic examination evaluations is made using the POP-Q measurement system on maximum Valsalva effort in the seated semi-lithotomy position (a 45° upright sitting position). Objective anatomical cure is defined as a Ba point < -1. Symptoms, quality of life and sexuality are evaluated with the Deutscher

Beckenboden-Fragebogen. This Pelvic Floor Questionnaire consists of four domains: bladder, bowel, pelvic organ prolapse and sexual function. In every domain various questions assess severity and condition-specific quality of life. Every question is scored on a scale from zero to four. The sum of each individual domain is divided by the maximum reachable score and multiplied by ten, giving a value between zero (0=no symptoms) and ten (10=maximum of symptoms) for each of the domains. Baessler et al. has published the results of the validation study and scoring system [11].

To evaluate nutrition status, patients will receive the "Mini Nutritional Assessment"-Fragebogen (<https://www.dgem.de/sites/default/files/PDFs/Screening/MNA-SF%20Deutsch-240513.pdf>) and laboratory testing of albumin, electrolytes (sodium, potassium, magnesium, phosphate, and calcium), haematocrit, creatinine, blood urea nitrogen, and bilirubin.

Patients will be asked to complete the standardised Visual Analog Scale (VAS), Numeric Rating Scale (NRS) [13] and answer the following questions:

- "Do you experience a sensation of bulging or protrusion from the vagina?" and "Do you have a bulge or something fallen out that you can see in the vagina?" [6]
- "Do you experience pain in the rump?" and "Do you experience pain in the lower back?" and "Do you experience pain while walking?" [6]
- "What rate of postoperative recurrence would you accept and still opt for the surgery?" [14].

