Furthermore, patients will answer the "Patient Global Impression of Improvement (PGI-I)" as it takes little effort for the patient and allows a precise result in terms of the rate of improvement after the operation [15]. One of the following answers can be given by each patient:

1. A lot better.
2. Much better.
3. A little better.
4. no change.
5. A little worse.
6. Much worse.
7. A lot worse.

Scheduled in-person follow-ups will occur at 4 to 6 weeks, 6 and 12 months after the operation. Each check-up will include a full urogynaecologic clinical examination including POP-Q, ultrasound and bloodwork as well as a written questionnaire identical to the one at baseline. In addition, an update of current medications, an assessment of new or continuing pelvic floor disorders and adverse events that occurred since the previous evaluation will be obtained by the study coordinator at each visit. All data will be anonymized and collected using case report forms by examiners or trained research coordinators who are blinded to the treatment assignment.

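### As written, the POP-Q mixed model has main effects only, so its single group coefficient averages over points and visits and tests no compartment

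*Combined protocol and SAP*

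**What the plan says.** The secondary hypothesis in section 2.1 is a "better rate anatomical outcome in each compartment (change in POP-Q values from baseline" for the Prolene group. Section 2.8 (Primary and secondary outcome measures) lists "the rate of suboptimal anatomical outcome in each compartment (POP-Q point, change in POP-Q values from baseline" among the secondary outcomes. Both work at the level of the compartment.

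Section 2.10 gives one analysis for these measurements: "Changes in POP-Q values from baseline over time will be analysed by a linear mixed model", specified as having "linear mixed model with fixed effects group, time, POP-Q point, age and BMI and random effect intercept per patient" where it lists its terms. It mentions no interaction, no separate model per point, no contrast and no time point for anatomy, and it does not list the points to be entered.

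The other analyses in section 2.10 do not cover POP-Q. The Chi-squared test is for adverse event rates. The comparison modelled on the primary outcome is for blood loss, pain killers and condition-specific quality of life. Metric variables are to be summarised descriptively.

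**The concern.** With group, time and point entered only as main effects, the model forces the group difference to be the same at every point and visit. The point terms compare points with each other; they do not compare the arms within a point. An analyst who follows the text gets one group estimate, while the hypothesis asks about each compartment.

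The distinction could matter in this trial. The randomised suture suspends the cervix from the sacrospinous ligament (section 2.6: "This suture will then be placed through the posterior cervical wall"), and eligibility refers to the apex ("Apical vaginal vault prolapse beyond the hymen (POP-Q point C >0) with a central defect") as well as the anterior wall. A difference could plausibly be larger at the apex than elsewhere. The pooled coefficient would then report a smaller number that belongs to no compartment, and effects in opposite directions could cancel. The size of the estimate would also depend on which points are entered, which the plan leaves open.

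This point concerns mean change only. The per-compartment rate has no cut-off other than "Objective anatomical cure is defined as a Ba point < -1" and no named test, which is a separate gap.

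**Working it through.** **The plan's own figure.** There is no POP-Q effect, SD or power in the documents. The only power statement (section 2.9) is for the primary outcome: SD of change = sqrt(2 × 2.2² × (1 − 0.5)) = 2.2, difference 2, 80% power. A two-sided t-test needs 20.002 per arm, so 21, with 82% power at 21. The figure reproduces. The 21 evaluable patients per arm are used below.

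**What the model estimates.** Written out, y = b0 + b1·group + time + point + age + BMI + u(patient) + error. The group difference is b1 at every point and visit. With complete data and ignoring covariates, b1 is the plain mean of the point-by-visit differences. With missing visits it is a weighted mean. Examples:

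- 2 cm at one of three points, constant over visits: 2/3 = 0.67 cm.
- 2 cm at C and D among six points: (2 + 2)/6 = 0.67 cm.
- −1.5 cm at two points and +1.5 cm at two others, of six: 0. A simulation of the stated model returned 0.00.

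This part needs no assumed SD.

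**What it may do to power.** All inputs here are assumptions: patient SD 0.8 cm; patient-by-point SD 1.5 for C and D and 0.8 for other points; residual SD 0.8; three visits; complete data; effect constant over visits; no gain from age, BMI or baseline. The three points are one apical and two others (Ba, C, Bp or Aa, C, Ba); the six are Aa, Ba, C, D, Ap, Bp.

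With balanced data the stated model equals a t-test on patient means over K points:

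- SD = sqrt(0.8² + Σ(point SD²)/K² + 0.8²/(3K)), and SE = SD × sqrt(2/21).
- K = 3: sqrt(0.64 + 3.53/9 + 0.64/9) = 1.050; SE 0.324.
- K = 6: sqrt(0.64 + 7.06/36 + 0.64/18) = 0.934; SE 0.288.
- C at 12 months only: sqrt(0.64 + 2.25 + 0.64) = 1.879; SE 0.580.

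Power from the noncentral t, 40 df, two-sided 0.05:

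| Effect at C | 1 cm | 1.5 cm | 2 cm |
|---|---|---|---|
| Pooled, 3 points, only C moves (coefficient 1/3 of effect) | 17% | 33% | 52% |
| Pooled, 3 points, others move a quarter as much (1/2) | 33% | 62% | 85% |
| Pooled, 3 points, others move half as much (2/3) | 52% | 85% | 98% |
| Pooled, 6 points, C and D move equally (1/3) | 20% | 40% | 62% |
| C alone at 12 months | 39% | 71% | 92% |

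If 1 cm applies at all points and visits, the pooled test has 85% (three points) or 92% (six), against 39% for C or 63% for Ba at 12 months (Ba: SD sqrt(3 × 0.64) = 1.386).

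**Sensitivity.** With all SDs 25% smaller or larger, at 2 cm: pooled with three points and only C moving, 76% to 36%; C at 12 months, 99% to 77%.

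**Precision and multiplicity of the alternative.** The 95% CI half-width for C at 12 months is 2.021 × 0.580 = 1.2 cm. Three uncorrected contrasts, if independent, give 1 − 0.95³ = 14.3%.

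**The case against.** The strongest reply is that pooling may be the better test. Section 2.1 expects benefit in every compartment, and if the other points move even half as much as C, the pooled coefficient beats C at 12 months at every effect size in the table. That stands. A reader might infer that the stated model is badly underpowered, or that it divides the effect by the number of points entered. The first is true only near the extreme in which one point moves and the rest do not; the second is true only if exactly one entered point is affected. The documents support neither pattern.

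A second reply is that interactions may have been intended, since the model is described in one sentence. That is possible, but nothing in the text says so.

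Third, descriptive means by group may show compartment differences. They may, but the plan names no between-group estimate with an interval and no test for them.

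A reader might also infer that the posterior compartment is not measured, because only Aa, Ba and C are named. That does not follow: the POP-Q system is adopted as a whole, and "Each check-up will include a full urogynaecologic clinical examination including POP-Q". What is missing is the list of points for the model.

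Finally, this is a secondary endpoint in a plan with one main hypothesis. That limits the weight of the point, but the stated analysis still does not answer the stated question.

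**Conclusion.** The point holds as a mismatch between hypothesis and model. Followed literally, section 2.10 yields one group coefficient averaged over points and visits, and no between-group estimate or test for any compartment or visit. This follows from the model equation and rests on no assumed value.

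The consequence for power is not fixed. At 2 cm at C with three points, it runs from a clear loss (52% against 92%) through near parity (85%) to a gain (98%), depending on how far the other points move. With six points and both C and D affected it is 62%. These figures rest entirely on assumed SDs and effect patterns and should be read as illustration.

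The plan should be corrected before unblinded analysis. The primary analysis and the sample size are unaffected.

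**What to change.** Name one POP-Q point per compartment in advance. For each, fit a repeated-measures model for change with group, visit, group-by-visit and the baseline value of that point; age and BMI may stay. Report one contrast per compartment, the group difference at 12 months with its 95% CI, labelled secondary and descriptive. Twelve months is suggested because it is the primary time point; the plan fixes none for anatomy.

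A single model with group-by-point-by-visit terms is an alternative, provided it has a patient-by-point random effect and point-specific variances. Adding interactions to the present patient intercept alone is not enough: in a simulation under the SDs assumed above, type I error was 10.4% for C at 12 months and 20.2% for C over visits.

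Keep the pooled coefficient as a global summary, because it is the stronger test when effects are similar. If interactions were always intended, writing them out settles most of this.

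The cost is SAP wording and a few more fits on data already collected. The downsides are lower power per compartment than the pooled test when effects are similar (39% or 63% against 85% to 92% for a uniform 1 cm, under the same assumptions) and up to 14.3% uncorrected familywise error over three contrasts, so none of them should be read as confirmatory.
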